## 11.1 Demographics

The demographics and baseline characteristics tables will include descriptive statistics for the following variables:

- Age (in years)
- Age categories: < 65 years,  $\geq$  65 years (65 – <75 years, 75 – <85 years,  $\geq$  85 years)
- Sex: Male, Female
- Race: White, Black or African American, Asian, American Indian or Alaska Native, Native Hawaiian or other Pacific Islander, Other, Not collected
- Ethnicity: Hispanic or Latino, Not Hispanic or Latino; Japanese, Not Japanese
- Height (cm)
- Weight (kg) at baseline
- BMI ( $\text{kg}/\text{m}^2$ ) at baseline
- Eastern Cooperative Oncology Group (ECOG) Performance Status: 0, 1 at baseline

Nicotine consumption will be described separately and will include descriptive statistics for the following variables:

- Nicotine use status
  - Never used
  - Regular user
  - Occasional user
  - Former user
- Duration of nicotine consumption (years) will be derived for nicotine user only: defined as (end date of nicotine consumption – start date of nicotine consumption + 1) / 365.25
- Only month and year will be collected in eCRF. As a result the day will be assumed to be the same for start and end date here. If month and year are missing, no imputation will be performed and if only month is missing, December 31th will be imputed for end date and January 1st will be imputed for start date for concerning the worst case of nicotine consumption. Duration of nicotine consumption will be presented by category:
  - Regular user: <5, 5-<10,  $\geq$ 10 years
  - Occasional user: <5, 5-<10,  $\geq$ 10 years
  - Former user: <5, 5-<10,  $\geq$ 10 years

The listing of demographics and baseline characteristics will include the following information: study cohort, subject identifier, age, sex, race, ethnicity, height (cm), weight (kg), BMI ( $\text{kg}/\text{m}^2$ ) and ECOG performance status at baseline. A separate listing of nicotine consumption will be created.

## 11.2 Medical History

Medical history will be coded using the latest available version of Medical Dictionary for Regulatory Activities (MedDRA). Medical history will be summarized as the numbers and percentages of participants by MedDRA preferred term (PT) as event category and MedDRA primary system organ class (SOC) as summary category. Each participant will be counted only once within each PT or SOC.

Medical history will be displayed in terms of frequency tables: ordered by primary SOC and PT in alphabetical order.

Listing of medical history data by participant will include coded terms and all the relevant data fields as collected on the “Medical History” eCRF page. This listing will be sorted by study cohort, subject identifier and then by start date.

## 11.3 Hepatitis B and C Serology

The results of the hepatitis B (HBsAg, HBsAb, HBcAb IgG and IgM), hepatitis C (HCVAb with reflex to HCV RNA) and human immunodeficiency virus (HIV) screening tests will be listed.

## 11.4 Disease History

Disease history is collected on “Urothelial Carcinoma Diagnosis”, “NSCL Cancer Diagnosis”, “Colorectal Cancer Diagnosis” and “Renal Cell Carcinoma Diagnosis” eCRF pages. Partial date will be imputed as described in the section 11.10.1.

The disease history table will include descriptive statistics for the following variables:

- Tumor sub-type
  - Renal pelvis
  - Ureter....
- Time since first diagnosis (years), defined as (the first study treatment date – the date of initial cancer diagnosis)/365.25
- Time since first metastatic disease diagnosis (years), defined as (the first study treatment date – the date of first occurrence of metastatic disease)/365.25
- Time since last disease progression (months), defined as (the first study treatment date - the date of last progression of disease)/30.4375
- Tumor Node Metastasis (TNM) Classification of Malignant Tumors at initial diagnosis
  - TX
  - T0
  - N1
  - ....

- TNM at study entry
  - TX
  - T0
  - N1
  - ...

Listing of disease history will be provided with all relevant data (as collected on the “Urothelial Carcinoma Diagnosis”, “NSCL Cancer Diagnosis”, “Colorectal Cancer Diagnosis” and “Renal Cell Carcinoma Diagnosis” eCRF pages) and derived variables used in the above table.

Additionally, listings of screening tumor biopsy and liquid biopsy data will be provided (as collected on the “Screening Tumor Biopsy” and “Liquid Biopsy” eCRF pages).

## **12**

## **Previous or Concomitant Medications/Procedures**

Prior and concomitant anti-cancer therapy / other medications will be coded using the latest available version of WHO Drug Dictionary and summarized based on the FAS by cohort and overall.

### **12.1**

### **Prior Anti-Cancer Therapies/Procedures**

The prior anti-cancer treatments and procedures are collected under the “Prior anti-cancer drug therapies details”, “Prior anti-cancer radiotherapies details” and “Prior anti-cancer surgeries details” eCRF pages.

The overall summary of presence of prior anti-cancer treatments and procedures table will include: the number and percentages of participants by type of treatment (by dose level and overall):

- participants with at least one type of prior anti-cancer treatment/procedure
- participants with at least one prior anti-cancer surgery
- participants with at least one prior anti-cancer drug therapy
- participants with at least one prior anti-cancer drug therapy for metastatic disease
- participants with at least one prior anti-cancer radiotherapy

For prior anti-cancer drug therapy, the following items will be summarized:

- Type of therapy: Anti-PD1 or Anti-PD-L1 / Cytotoxic Therapy / Monoclonal Antibodies Therapy/ Small Molecules / Immunotherapy except Anti-PD-1 or Anti-PD-L1 / Endocrine Therapy/Other
- Intent of therapy: Adjuvant / Neoadjuvant / Metastatic/ Locally advanced
- For Metastatic/ Locally advanced intent, the therapy lines: 1 / 2 / 3 /  $\geq 4$
- Best response: Complete Response (CR) / Partial Response (PR) / Stable Disease (SD)/ Progressive Disease (PD) / Non-Complete Response/Non-Progressive Disease (Non-CR/Non-

PD)/ Not evaluable (NE) / Unknown / Not applicable. Best response is derived from the last treatment regimen.

The prior anti-cancer drugs will also be extensively detailed with the number and percentage of participants by the drug class and PT in a separate table. A participant will be counted only once within a given drug class and within a given drug name, even if the participant received the same medication at different times. The summary tables will be sorted on decreasing frequency of drug class and decreasing frequency of drug name in a given drug class, based on the incidence in the “Overall” column. In case of equal frequency regarding drug class (respectively drug name), alphabetical order will be used.

The listings of prior anti-cancer treatments and procedures will also be provided:

- listing of prior anti-cancer drug therapies
- listing of prior anti-cancer radiotherapy
- listing of prior anti-cancer surgeries

These will include study cohort, subject identifier, and all the relevant collected data-fields on the corresponding eCRF pages (ordered by study cohort, subject identifier and therapy start date).

## 12.2 Previous and Concomitant Medications/Procedures

Previous and concomitant medications are collected on the “Relevant previous medications details” and “Concomitant medications details” eCRF page. Prior and concomitant procedures are collected on the “Concomitant procedures details” eCRF page.

**Previous medications** are medications, other than study medications and pre-medications for study drug, which are started before first dose date of study treatment.

**Concomitant medications** are medications, other than study medications and pre-medications for study drug, which started prior to first dose date of study treatment and continued during the on-treatment period as well as those started during the on-treatment period.

Previous medications and Concomitant medications will be summarized separately showing the number of participants and percentages by drug class and preferred term by dose level and overall. A participant will be counted only once within a given drug class and within a given drug name, even if the participant received the same medication at different times.

The summary tables will be sorted on decreasing frequency of drug class and decreasing frequency of drug name in a given drug class, based on the incidence in the “Overall” column. In case of equal frequency regarding drug class (respectively drug name), alphabetical order will be used.

Previous and concomitant medication data will be listed separately. Following variables will be included in the listings: study cohort, subject identifier, and all corresponding collected data-field

on the corresponding eCRF page. The listings will be sorted by study cohort, subject identifier, and the start date of the medication.

Prior and concomitant procedures data will be listed from the “Concomitant procedures details” eCRF page. Study cohort, subject identifier, and all collected data-field on the corresponding eCRF page will be included in the Prior and Concomitant Procedure listing. The listings will be sorted by study cohort, subject identifier, and the start date of the procedure.

Premedication data (reported on the “Premedication details” eCRF page) given before the study drug administration will be listed.

### **12.3 Subsequent Anti-Cancer Therapies/Procedures**

Number of participants received treatment after discontinuation will be summarized as reported on the “Anti-Cancer Treatment after Discontinuation Details”, “Radiotherapy after Discontinuation Details” and “Surgery after Discontinuation Details” eCRF pages.

Number and percentage of participants with any anti-cancer treatment after discontinuation will be tabulated by cohort and overall based on the data collected from the “Anti-Cancer Treatment Details” eCRF pages, as following:

- Type of therapies (as collected in eCRF):
- Anti-PD-1/anti-PD-L1,
- Cytotoxic Therapy,
- Endocrine Therapy,
- Monoclonal Antibodies therapy,
- Small molecules,
- Immunotherapy except Anti-PD-1/anti-PD-L1,
- Other.

Summary statistics will be created for best response across all post study treatments based on the data collected from “Anti-Cancer Treatment Details” eCRF page, i.e. CR / PR / PD / SD / Non-CR/Non-PD / Unknown / Not evaluable / Not applicable.

Anti-cancer treatment after discontinuation will be provided in a listing with data retrieved from “Anti-Cancer Treatment after Discontinuation Details”, “Radiotherapy after Discontinuation Details” and “Surgery after Discontinuation Details” eCRF pages.

### **13 Study intervention Compliance and Exposure**

All dosing calculations and summaries, as well as the listings of study drug administration will be based on ‘NHS-IL12 Administration’ and ‘Avelumab Administration’ eCRF pages.

Based on review of available safety, PK, and pharmacodynamics data, the dose for the expansion cohorts receiving combination therapy will be avelumab 800 mg once weekly for the first 12 weeks in combination with M9241 16.8  $\mu$ g/kg once every 4 weeks, then continuation with the combination of avelumab at 800 mg once every 2 weeks and M9241 at 16.8  $\mu$ g/kg once every 4 weeks. The dose for participants receiving avelumab weekly induction monotherapy in Stage 2 of the UC expansion cohort will be avelumab 800 mg once weekly for the first 12 weeks, then avelumab at 800 mg once every 2 weeks.

## 13.1 Exposure to Study Drug

### 13.1.1 Avelumab

The calculations described on this point will use all information before treatment re-initiation. Treatment re-initiation will be listed.

The actual dose level for avelumab is 800 mg.

The duration of avelumab treatment (in weeks) during the study for a participant will be based on the duration of the cycle of 28 days and is defined as:

$$\text{Treatment duration (weeks)} = (\text{end date of last cycle} - \text{first dose date} + 1)/7$$

The end date of last cycle for avelumab is defined as follows:

- if the last dose is given at the day 1 of the cycle then the end date of the last cycle will be the date of the last dose + 28 days -1
- if the last dose is given at the day 8 of the cycle then the end date of the last cycle will be the date of the last dose + 21 days -1 (only applicable for the first 3 cycles)
- if the last dose is given at the day 15 of the cycle then the end date of the last cycle will be the date of the last dose + 14 days -1
- if the last dose is given at the day 22 of the cycle then the end date of the last cycle will be the date of the last dose + 7 days -1 (only applicable for the first 3 cycles)

The cumulative dose (mg/kg) of avelumab per participant in a time period is the sum of the actual dose that the participant received within that period.

The dose intensity (DI) and the relative dose intensity (RDI) will be calculated for each participant across all cycles. The dose intensity per cycle (mg/cycle) is defined as

$$\text{DI (mg/cycle)} = \text{Cumulative dose (mg)}/[\text{treatment duration (in weeks)}/4]$$

The relative dose intensity (RDI) is defined as the actual dose intensity divided by the planned dose per cycle and expressed in %.

$$\text{RDI (\%)} = 100 \times [\text{DI (mg/cycle)}/(\text{planned dose} \times 2) \text{ (mg/cycle)}]$$

The planned dose for the expansion cohorts receiving combination therapy will be avelumab 800 mg once weekly for the first 12 weeks in combination with M9241 16.8 µg/kg once every 4 weeks, then continuation with the combination of avelumab at 800 mg once every 2 weeks and M9241 at 16.8 µg/kg once every 4 weeks.

The summary of treatment exposure and compliance for avelumab will include the following information:

- Treatment duration (weeks)
- Total number of infusions received
- Cumulative dose (mg))
- Dose intensity (mg/cycle)
- Relative dose intensity (%)
  - <50%
  - [50%, 65%[
  - [65%, 80%[
  - [80%, 100%]
  - > 100%

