### 8.5.4 Analysis of Safety and Other Endpoints

The extent of exposure to avelumab and M9241 will be characterized by duration (weeks), number of administrations, cumulative dose ( $\mu\text{g}/\text{kg}$ ), dose intensity ( $\text{mg}/\text{kg}/\text{week}$ ), relative dose intensity (actual dose given/planned dose), and number of dose delays.

Safety analyses will be performed on the Safety Analysis Set. The safety endpoints will be tabulated by dose-level, using descriptive statistics.

Safety assessments will be based on review of the incidence of AEs, including AEs of special interest, TRAEs, and changes in vital signs, ECGs, body weight, and laboratory values (hematology and serum chemistry).

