## 15 Treatment Compliance and Exposure

All dosing calculations and summaries, as well as the listings of study drug administration will be based on ‘NHS-IL12 Administration’ and ‘Avelumab Administration’ eCRF pages.

For the the dose levels 4 µg/kg, 8 µg/kg, 12 µg/kg, 16.8 µg/kg: Avelumab administered as IV infusion at a dose of 10 mg/kg once every 2 weeks will be administered on Day 1 and Day 15 of each 28-day (4 weeks) cycle. NHS-IL12 will be administered in escalating doses of 2, 4, 8, 12, 16.8 µg/kg at a starting dose level of 4 µg/kg by subcutaneous injection only on Day 1 of each cycle, immediately prior to avelumab infusion.

For the avelumab once weekly cohort: In addition to the above NHS-IL12 escalation cohorts, an avelumab once weekly cohort will be opened. For this cohort, subjects will receive avelumab at 800 mg once weekly for the first 12 weeks in combination with NHS-IL12 at the NHS-IL12 MTD once every 4 weeks, then avelumab at 800 mg once every 2 weeks plus NHS-IL12 at the NHS-IL12 MTD once every 4 weeks until a criterion for treatment discontinuation has been met.

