$$DI \text{ (mg/kg/cycle)} = \text{Cumulative dose (mg/kg)} / [\text{treatment duration (in weeks)} / 4]$$

For the subjects in the avelumab once weekly cohort, the dose intensity per cycle (mg/cycle) is defined as

$$DI \text{ (mg/cycle)} = \text{Cumulative dose (mg)} / [\text{treatment duration (in weeks)} / 4]$$

The relative dose intensity (RDI), with the exception of the avelumab once weekly cohort, is defined as the actual dose intensity divided by the planned dose per cycle and expressed in %.

$$RDI \text{ (\%)} = 100 \times [DI \text{ (mg/kg/cycle)} / (\text{planned dose} \times 2) \text{ (mg/kg/cycle)}]$$

For the subjects in the avelumab once weekly cohort, the relative dose intensity (RDI) is defined as

$$\text{RDI (\%)} = 100 \times [\text{DI (mg/cycle)} / (\text{planned dose} \times 2) \text{ (mg/cycle)}]$$

The summary of treatment exposure and compliance for avelumab will include the following information:

- Treatment duration (weeks)
- Total number of infusions received
- Cumulative dose (mg/kg)
- Dose intensity (mg/kg/cycle)
- Relative dose intensity (%)
  - <50%
  - [50% , 65%[
  - [65% , 80%[
  - [80% , 100%]
  - > 100%

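### Avelumab relative dose intensity under weekly induction is divided by two doses per cycle, although four are planned in cycles 1 to 3, so full dosing reads 200%

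*SAP*

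**What the plan says.** Two analysis plans are involved: the SAP for dose escalation and the Integrated Analysis Plan (IAP) for the expansion cohorts.

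IAP 13.1.1 gives the definition in words: "The relative dose intensity (RDI) is defined as the actual dose intensity divided by the planned dose per cycle and expressed in" per cent. The formula beneath it is RDI = 100 × DI / (planned dose × 2), in mg per cycle, with DI and RDI computed once per participant across all cycles. The section opens with "The actual dose level for avelumab is 800 mg". It describes the planned regimen as "800 mg once weekly for the first 12 weeks in combination with M9241", followed by 800 mg every two weeks. Its rule for the end of the last cycle provides for Day 8 and Day 22 infusions. For Day 22 the end date is the "date of the last dose + 7 days -1 (only applicable for the first 3 cycles").

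Section 15.1.1 of the dose-escalation SAP has a separate line for its weekly cohort, "For the subjects in the avelumab once weekly cohort, the relative dose intensity (RDI) is defined as", and the formula that follows again uses planned dose × 2. Section 15 of that SAP sets the schedule for the cohort: "subjects will receive avelumab at 800 mg once weekly for the first 12 weeks in combination with NHS-IL12".

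Protocol 8.5.4 lists the exposure measures, among them "relative dose intensity (actual dose given/planned dose), and number of dose delays".

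Both plans report RDI in five bands: below 50%, 50 to <65%, 65 to <80%, 80 to 100%, and above 100%.

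**The concern.** A factor of 2 is right for infusions on Day 1 and Day 15 only. Under weekly induction there are four infusions in each of the first three cycles, so the formula's denominator is half the planned dose for that period. The formula then matches neither the verbal definition just above it nor the protocol's ratio of dose given to dose planned. It looks carried over from the two-weekly cohorts: IAP 13.1.1 still labels the cumulative flat dose in mg/kg.

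At stake is the compliance part of the exposure table. The first on-treatment scan is at the end of Cycle 2 (Protocol Table 5), so participants who stop for progression at that scan fall where the inflation is largest. For them the bands cannot separate full dosing from substantial under-dosing, and marked under-dosing can look adequate. M9241 RDI (IAP 13.1.2) uses the correct planned dose per cycle, so a fully compliant participant on the combination would show 100% for M9241 beside 200% for avelumab. Protocol 3.6.3 introduced the weekly regimen to help maintain avelumab exposure, and RDI is the planned summary of whether that intensity was delivered.

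**Working it through.** **Inputs.** Dose 800 mg; cycle 28 days; weekly dosing for 12 weeks, then two-weekly; DI = cumulative dose / (D/4), where D is treatment duration in weeks to the end of the last cycle (all IAP 13.1.1; the once-weekly cohort in SAP 15 and 15.1.1 is the same). Let n be the doses received and k = D/4 the duration in cycles.

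**The plan's denominator.** 2 × 800 = 1600 mg per cycle. This agrees with the schedule from cycle 4 onward. It is also right for the 10 mg/kg two-weekly cohorts: 12 infusions over 24 weeks give DI = 120/6 = 20 mg/kg/cycle, and 20/(10 × 2) = 100%. It does not agree in cycles 1 to 3, where the schedule gives 4 × 800 = 3200 mg.

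**Plan formula.** RDI = 100 × [800n/(D/4)]/1600 = 100 × 2n/D.

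**Schedule-based formula.** Scheduled doses S = min(D, 12) + max(D − 12, 0)/2, and RDI = 100 × n/S.

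**Ratio of the two.** It equals 2S/D. For D ≤ 12, S = D and the ratio is 2. For D ≥ 12, S = 12 + (D − 12)/2, so 2S/D = (D + 12)/D = 1 + 12/D = 1 + 3/k. Because n cancels, this holds at any level of compliance.

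| D (weeks) | n | S | RDI as written | Band | RDI against schedule | Band |
|---|---|---|---|---|---|---|
| 12 | 12 | 12 | 200% | >100 | 100% | 80–100 |
| 16 | 14 | 14 | 175% | >100 | 100% | 80–100 |
| 24 | 18 | 18 | 150% | >100 | 100% | 80–100 |
| 48 | 30 | 30 | 125% | >100 | 100% | 80–100 |
| 12 | 7 | 12 | 116.7% | >100 | 58.3% | 50–<65 |
| 12 | 6 | 12 | 100% | 80–100 | 50% | 50–<65 |
| 12 | 5 | 12 | 83.3% | 80–100 | 41.7% | <50 |
| 12 | 3 | 12 | 50% | 50–<65 | 25% | <50 |
| 24 | 9 | 18 | 75% | 65–<80 | 50% | 50–<65 |
| 48 | 15 | 30 | 62.5% | 50–<65 | 50% | 50–<65 |
| 48 | 24 | 30 | 100% | 80–100 | 80% | 80–100 |
| 16 | 12 | 14 | 150% | >100 | 85.7% | 80–100 |
| 4 | 1 | 4 | 50% | 50–<65 | 25% | <50 |
| 4 | 2 | 4 | 100% | 80–100 | 50% | 50–<65 |

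The row with 12 doses over 16 weeks is a delay: the written formula hides it, the schedule-based one shows it. The last two rows are participants who stop after Cycle 1 Day 1 and after Cycle 1 Day 8.

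**Bands.** Dividing the cut-points 50, 65, 80 and 100% by the ratio gives the values they really mark: 25, 32.5, 40 and 50% through cycle 3; 33.3, 43.3, 53.3 and 66.7% at six cycles; 40, 52, 64 and 80% at twelve.

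**The case against.** **The term may mean something else.** Neither plan prints 1600 mg, and the IAP sentence after the formula describes the planned dose as the whole schedule. If planned dose meant the amount due per two weeks, doubling it would give 3200 mg in induction and 1600 mg later, which is correct. Neither plan states that reading. Both plans define a dose reduction as a non-zero dose below 90% of the planned dose (SAP 15.2, IAP 13.2), which compares a single administration. Even on the generous reading, the formula has one planned dose for a ratio taken across all cycles, so it has no defined value for a participant who continues past cycle 3.

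**RDI is one descriptive line.** This is true. Dose reductions, delays and interruptions are summarised separately, dose intensity itself is correct, and a value near 200% on a flat dose would probably prompt a question. That limits the harm. It does not cover cases such as 83.3%, which look plausible and are wrong.

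**The affected group may be small.** The IAP modification history records that the study was stopped early after the futility analysis. UC Stage 1 had 16 participants, and the weekly dose-escalation cohort planned up to 6. The documents do not say how many others were treated, nor how often under-dosing of the kind tabulated occurred. Those examples illustrate the formula and are not observed data.

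**A schedule-based RDI also reads low for mid-cycle stops.** This stands. D runs to the end of the 28-day cycle, so a participant who received every dose due and stopped after Cycle 1 Day 1 reads 25%, and one who stopped after Cycle 3 Day 1 (9 doses over 12 weeks) reads 75%. That comes from the plan's own duration rule and is separate from the factor of 2.

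**Conclusion.** The formula is wrong as written in both plans. For avelumab under weekly induction it overstates RDI by exactly 2 up to three cycles and by 1 + 3/k at k cycles after that: 1.75 at four, 1.5 at six, 1.25 at twelve. Every participant who receives the full schedule over completed cycles is reported above 100%. Over three cycles, anything from 7 to 12 of 12 doses (58.3% to 100%) falls in that one band. Not everyone changes band, as 24 of 30 doses over twelve cycles shows, and the inflation shrinks with longer treatment.

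The result rests on reading planned dose as one 800 mg infusion and on taking treatment duration as the plans define it. The effect is limited to the RDI value and its bands. It should be corrected before the exposure tables are produced, but it does not touch any efficacy or adverse event result.

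**What to change.** In IAP 13.1.1, and in SAP 15.1.1 for the once-weekly cohort, replace the formula with:

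RDI (%) = 100 × cumulative dose (mg) / planned cumulative dose (mg),

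where planned cumulative dose = 800 × [min(D, 12) + max(D − 12, 0)/2] mg and D is treatment duration in weeks as already defined. This is 3200 mg per 28 days for the first 12 weeks and 1600 mg per 28 days afterwards. Full dosing over completed cycles then reads 100% at any duration, and delays still lower the value.

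Add a table footnote that duration runs to the end of the last cycle, so participants who stop mid-cycle read below 100% even if they missed no dose. Leave the formula for the two-weekly 10 mg/kg cohorts as it is.

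The cost is one formula in each plan, the matching program change and a footnote. No new data are needed, and the change takes no position on the dose.
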